12.7.7 TtR and iTtR

TtR/iTtR will be summarized using Kaplan-Meier estimates for each indication separately. A sensitivity analysis will be performed using the ASaT population. Patients with missing data will be censored at the last tumor assessment date, date of death, or date of first dose of study treatment (if incomplete or no baseline tumor assessments), whichever occurs latest.

12.7.8 CTC Response

The CTC response will be summarized using descriptive statistics (frequency and percentage) together with a 95% CI for the mCRPC indication cohort. Patients with missing data will be considered as non-responders.

12.7.9 PSA Response

The PSA response will be summarized using descriptive statistics (frequency and percentage) together with a 95% CI for the mCRPC indication cohort.

Responses will need confirmation by a second consecutive value obtained 4 or more weeks after the first value indicated a response. Evaluable patients with no confirmed response as defined above will be classified as non-responders.

12.7.10 Time to Confirmed PSA Progression

Time to confirmed PSA progression will be summarized using Kaplan-Meier estimates for the mCRPC indication. Patients with missing data will be censored at the PSA assessment date, date of death, or date of first dose of study treatment (if incomplete or no baseline PSA assessments), whichever occurs latest.

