### 1.3.3 Collection of blood samples, nanrilkefusp alfa combined with pembrolizumab

All attempts should be made to collect the samples on time.

Cycle	Screening	Cycle 1						Cycle 2					Cycle 3				From cycle 4				End of treatment
		1	2	6	8	9	13	1	2	6	8	9	1	2	8	9	1	2	8	9	
Nanrilkefusp alfa administration 		X	X		X	X		X	X		X	X	X	X	X	X	X	X	X	X	
Pembrolizumab administration 		X						X					X				X				
Serum for nanrilkefusp alfa PK													See section 1.3.5								
Serum for cytokines 		X	X		X	X		X	X		X	X									
Serum for nanrilkefusp alfa immunogenicity 		X						X									Cycle 4 only				X
Serum for pembrolizumab PK 		X						X									Cycles 4 and 8 only				X
Serum for pembrolizumab immunogenicity 		X						X									Cycle 4 only				X
Whole blood for RNA and DNA analysis 		X		X				X		X											
HIV, HBV, and HCV	X																				
Hematology (full complete blood count including absolute lymphocyte count)	X	X 	X 	X	X 	X 	X	X 		X	X 		X 		X 		X 		X 		X
Biochemistry (including C-reactive protein)	X	X 	X 	X		X 	X	X 		X		X 	X 		X 		X 		X 		X
Creatinine clearance	X	X 		X		X 		X 		X		X 	X 		X 		X 		X 		
C-reactive protein				X 					X 		X 										
Coagulation	X	X 		X 				X 		X 			X 		X 		X 		X 		X
TSH, T3 or free T3, free T4	X	X 											X 				X 				X
Patients with mCRPC: PSA, alkaline phosphatase, lactate dehydrogenase, CTCs, circulating tumor DNA fraction	X		X 										X 				X 				
Serum pregnancy	X																				

1. Time to be recorded
2. Time to be recorded; pembrolizumab will be administered within 30 minutes following nanrilkefusp alfa administration.
3. Before nanrilkefusp alfa administration and 4 hours ( $\pm 30$  min) after nanrilkefusp alfa administration
4. Within 1 day before nanrilkefusp alfa administration

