### 1.3.4 Collection of blood samples, for patients who continue pembrolizumab after discontinuation of nantilkefusp alfa

All attempts should be made to collect the samples on time.

Cycle	From cycle 1	End of treatment
Day	1	
Pembrolizumab administration 	X	
Hematology	X 	X
Biochemistry	X 	X
Coagulation	X 	X
TSH, T3 or free T3, free T4	X 	X

1. Time to be recorded
2. Before pembrolizumab administration
3. Every other cycle

*T3, triiodothyronine; T4, thyroxine; TSH, thyroid stimulating hormone*

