#### 4.1.3 Follow-up

All patients will come to the clinic 30 ( $\pm 2$ ) days and 90 ( $\pm 2$ ) days after their last dose of nanrilkefusp alfa and/or pembrolizumab (whichever occurs later).

Patients will be followed up for survival every 3 months ( $\pm 2$  weeks) during year 1 and then every 6 months ( $\pm 2$  weeks) until the end of the study.

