- Time to confirmed PSA progression

Time to confirmed PSA progression is defined as the time from the first day of study treatment to the date of PSA progression and will be summarized using Kaplan-Meier estimates for the mCRPC indication.

PSA progression is defined as the date when an increase of 25% or more and an absolute increase of 2 ng/mL or more from the nadir are documented. For patients who have a decline in PSA during treatment, PSA progression must be confirmed by a second value 3 or more weeks later increased with respect to the nadir PSA.

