10.13.12 Time to Confirmed PSA Progression

Time to confirmed PSA progression is defined as the time from the first day of study treatment to the date of PSA progression, where PSA progression is defined as the date when an increase of 25% or more and an absolute increase of 2 ng/mL or more from the nadir (or baseline, whichever is lowest) are documented.

For patients who have a decline in PSA during treatment, PSA progression must be confirmed by a second value 3 or more weeks later increased with respect to the nadir PSA (or baseline, whichever is lowest). The date of the first PSA progression will be used; in patients with an unconfirmed PSA progression, date of the first PSA progression will be used if followed by treatment discontinuation.

This endpoint applies to the mCRPC cohort only.

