12.7.6 PFS and iPFS

PFS/iPFS will be summarized using Kaplan-Meier estimates for each indication separately. A sensitivity analysis will be performed using the ASaT population.

PFS will be calculated based on PCWG3-modified RECIST for the mCRPC cohort for those patients with both measurable and non-measurable disease.

Patients with missing data will be censored/considered as having an event as specified below:

Situation	Date of progression or censoring	Outcome
Incomplete or no baseline tumor assessments.	Date of the first day of study treatment	Censored
Start of new anti-cancer therapy.	Date of the last tumor assessment with non-progression before the start of new anti-cancer therapy.	Censored
Death before the first disease progression assessment.	Date of death.	Progressed

Situation	Date of progression or censoring	Outcome
Death between adequate tumor assessment visits.	Date of death.	Progressed
Progression or death after one (consecutively) missed adequate tumor assessment ^a .	Date of progression or death, whichever is earliest (if both occur).	Progressed
Progression or death after more than one (consecutively) missed adequate tumor assessments.	Date of the last evaluable tumor assessment.	Censored
No progression, no death.	Date of the last evaluable tumor assessment, or first date of study treatment if no post-baseline tumor assessments.	Censored

^aIdentified as 12 weeks between the date of last evaluable tumor assessment and the date of the event.

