12.8.5.5 Long Term Follow-up

Survival status data will be listed for the ASaT population. Additionally, all subsequent anti-cancer therapy will be summarized and listed.

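### SAP 12.7.10 lets a later death set the censoring date for time to confirmed PSA progression, so the mCRPC Kaplan-Meier curve is never lower, and can be higher, than with censoring at the last PSA

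*SAP*

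**What the plan says.** Protocol 9.3.3.2 defines the endpoint: "Time to confirmed PSA progression is defined as the time from the first day of study treatment to the date of PSA progression". It asks for Kaplan-Meier estimates in mCRPC and gives no censoring rule for this endpoint.

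SAP 10.13.12 keeps that event definition, so death is not an event. It adds that "in patients with an unconfirmed PSA progression, date of the first PSA progression will be used if followed by treatment discontinuation".

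SAP 12.7.10 supplies the only censoring rule: "Patients with missing data will be censored at the PSA assessment date, date of death, or date of first dose of study treatment". The latest of the three dates applies. The bracketed condition about baseline PSA attaches only to the first-dose option.

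Three other places matter:

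- **PSA sampling.** Protocol 1.3.3 has one row for "Patients with mCRPC: PSA, alkaline phosphatase, lactate dehydrogenase, CTCs, circulating tumor DNA fraction". It is marked at screening and in treatment cycles, every other cycle from cycle 4, with no End-of-treatment mark as the table reached us. Protocol 1.3.4, the blood schedule for patients continuing on pembrolizumab alone, has no PSA row.
- **Deaths.** Protocol 4.1.3: "Patients will be followed up for survival every 3 months" in year 1, then six-monthly to study end. Overall survival will no longer be reported, but SAP 12.8.5.5 still states: "Survival status data will be listed for the ASaT population".
- **PFS.** For a patient with neither progression nor death, SAP 12.7.6 censors at: "Date of the last evaluable tumor assessment, or first date of study treatment if no post-baseline tumor assessments".

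**The concern.** Kaplan-Meier treats every patient in the risk set as someone whose event would have been recorded had it happened. Between the last PSA sample and death that is not so. If such a patient is censored at death, those unobserved weeks count as time free of PSA progression. Follow-up is lengthened only for patients who die; those who stay alive are censored at their PSA date.

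At stake are the mCRPC PSA-progression curve, its quartiles and its median. They would look at least as good as the PSA data support, and a median that would otherwise be reached could be reported as not reached.

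**Working it through.** The plan states no PSA-progression rate, event count or median, so there is no figure to reproduce. The check has three parts.

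**1. Direction.** The estimator is S(t) = Π (1 − d_j / n_j) over event times up to t. The censoring rule does not change which patients have events or when, so each d_j is fixed. Moving a censoring date from the last PSA to a later death can only leave n_j the same or raise it. Each factor, and so S(t), stays level or rises. This needs no assumed rates.

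**2. Ten-patient illustration (invented data).** Events fall at weeks 12, 12, 18 and 24. Four patients have their last PSA at weeks 6, 6, 12 and 12 and die at weeks 30-44. Two are alive and still sampled beyond week 24.

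- Censored at last PSA: 6/8 × 3/4 × 2/3 = 0.375 at week 24; median 24 weeks.
- Censored at death: 8/10 × 7/8 × 6/7 = 0.600; median not reached.

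If every death comes before the next scheduled PSA, the two rules agree (0.382 under both in a simulated check). The effect comes from deaths after sampling has stopped or been missed.

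**3. Size by simulation.** From the documents: every other 3-week cycle, so sampling every 2 × 3 = 6 weeks. Assumed: exponential PSA progression with median 12 or 18 weeks, so the true week-24 rate is 2^(−24/12) = 25% or 2^(−24/18) = 39.7%, about 40%; exponential treatment stop with median 12 or 18 weeks; a stated share of patients seen to die at an exponential lag after stopping. Every rise seen by the last sample counts as an event, which gives SAP 10.13.12 its full effect. There were 300,000-400,000 patients per setting. The table shows the week-24 Kaplan-Meier estimate.

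| Setting | True 25%: last PSA / SAP rule | True 40%: last PSA / SAP rule |
|---|---|---|
| Independent stop, no End-of-treatment PSA, 30-60% die, median lag 15-30 weeks | 25% / 33-50% | 40% / 47-61% |
| Same, 10-60% die, lag 8-30 weeks | 25% / 27-50% | 40% / 41-61% |
| PSA added 1 week after stop, 30-60% die, lag 15-30 weeks | 21-22% / 28-40% | 35-36% / 42-53% |
| PSA added 1 week after stop, 10% die, lag 8-30 weeks | 21-22% / 23-25% | 35-36% / 37-39% |
| No End-of-treatment PSA, 30-60% die, stop correlated 0.3 with PSA progression | 30-33% / 37-55% | 47-49% / 53-67% |
| Same, correlation 0.6 | 36-42% / 42-61% | 55-61% / 60-75% |

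The first four rows were re-run independently for this write-up and agree.

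**The case against.** **The rule is worded for patients with missing data.** True, and that term is not defined. But no other rule covers patients without PSA progression. Either this sentence covers them or nothing does, and it also omits which PSA date is meant.

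**The sampling premise rests on a table with uncertain alignment.** This stands in part. The marks in the PSA row may have shifted in extraction, so an End-of-treatment sample cannot be ruled out. The direction against last-PSA censoring does not depend on it; the size does.

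**SAP 10.13.12 already turns unconfirmed rises before discontinuation into events.** It does, and the simulation credits it fully. It cannot help a patient with no rise by the last sample.

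**PFS is not a clean comparator.** Fair: death is an event for PFS and not here. The comparison shows only that the SAP elsewhere ends follow-up at the last assessment when no event has been seen.

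**Death precludes PSA progression, so censoring at the last PSA is not ideal either.** Also fair. It still censors patients who later die, and any link between treatment stop and PSA progression remains.

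A reader might also extend the criticism to time to response, whose rule in SAP 12.7.7 has the same structure. The documents do not support that step. Protocol 9.3.1 and 9.3.3.2 themselves specify Kaplan-Meier and that censoring for time to response. Response is a favourable event, so a later censoring date lowers the estimated response rate. A different summary there would be a preference.

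**Conclusion.** The rule as written keeps patients at risk while they cannot be observed. Against censoring at the last PSA, the curve and median are equal or more favourable. That much is certain, given the reading that the sentence covers patients without PSA progression.

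A reader might infer that the rule always overstates the truth. That does not follow. With independent treatment stop and no End-of-treatment PSA, a true 25% reads about 27-50% and a true 40% about 41-61%. With an End-of-treatment PSA and 10% of patients dying, the rule reads 23-25% and 37-39%, at or slightly below the truth and nearer to it than last-PSA censoring. None of these rates is in the documents. SAP 6.1 reports that recruitment stopped after the August 2023 futility analysis, and the actual mCRPC cohort size is not given, so no cohort-level figure is offered.

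Impact is low. The endpoint is secondary and descriptive, in one cohort, with no hypothesis test. The primary ORR and the futility criteria do not use it.

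**What to change.** In SAP 12.7.10, censor patients without PSA progression at the last evaluable PSA assessment, or at first dose if there is no baseline or no post-baseline PSA. Remove the date of death as a censoring date. Replace the reference to missing data with patients without PSA progression, and say that the last PSA date is meant.

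Record the change, its timing and its reason in SAP 6.1 before database lock; it would come after the futility analysis in an open-label study. State there that it removes only the effect of the death date, not any bias from treatment stop being related to PSA progression.

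The cost is a short change of SAP wording and minor programming. No new data are needed, and no protocol text is contradicted, because the protocol sets no censoring rule for this endpoint.

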12.7.11 OS – Exploratory Analysis: Not to be reported

OS will be summarized using Kaplan-Meier estimates for each indication separately. Patients with missing data will be censored at the last time known to be alive. OS will be analyzed on the ASaT and Efficacy Populations.

12.7.11.1 Duration of Follow-up – Exploratory Analysis: Not to be reported

A reverse Kaplan-Meier analysis will be performed on OS to estimate the median follow-up incorporating censoring rules and flipping event/censored events.

12.7.12 PFS2 – Exploratory Analysis: Not to be reported

PFS2 will be summarized using Kaplan-Meier estimates for each indication separately for all patients in the ASaT and Efficacy populations.

Patients alive and for whom a second disease progression has not been observed will be censored at the last time known to be alive and without second objective disease progression. Death is considered an event, regardless of whether subsequent anti-cancer therapy has been started. Patients progressing on subsequent anti-cancer therapy without experiencing progression on SOT101 will also be considered to have experienced an event.

12.8 Safety Analyses

AEs will be graded according to the NCI CTCAE version 5.0.

All safety analyses will be summarized separately for each indication and overall. Safety analyses will be performed in the ASaT population unless otherwise specified.

12.8.1 Adverse Events

AEs will be coded according to MedDRA (Version 24.1 or later) by SOC, PT, and severity grade using NCI CTCAE version 5.0.

Linked AEs will be identified via the AE ID recorded as change in severity of an existing AE on the AE CRF page. Multiple AE records with differing attributes can comprise a single linked AE occurrence. Linked AEs will be selected for analysis in tables based on their worst case scenario attribute e.g. maximum CTC grade, causal relationship, seriousness, and treatment emergence out of all records.

The ordering (the worst to best) for the following characteristics will be applied:

- Relationship: suspected, not suspected.
- Toxicity Grade: Grade 5 to Grade 1.

In the case of multiple actions taken across linked AEs, the AEs will appear in all relevant tables, however for the figures the worst case shall be taken based on the following hierarchy:

- Action taken with SOT101: permanently discontinued, temporarily discontinued, dose reduced, other action, no action taken.
- Action taken with pembrolizumab: permanently discontinued, delay of administration, other action, no action taken.

AE records within a linked AE can be given different treatment-emergence status. Treatment emergence for linked AEs will be established as those records in the linked AE with a worsening of severity from the preceding pre-treatment record. Any AE subsequently linked to an on-treatment AE would be considered treatment-emergent.

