7. Performance status: Eastern Cooperative Oncology Group (ECOG) performance score 0-1
8. Must have recovered from all AEs (except alopecia) due to previous therapies to grade  $\leq 1$  toxicity (excluding alopecia) or have stable grade 2 neuropathy

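### TEAE tables grade a linked AE on its pre-dose records too, so a grade 3 that eased before dosing and rose only to grade 2 on treatment is reported as a grade 3 TEAE

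*SAP*

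**What the plan says.** SAP 12.8.1 links AE records through the AE identifier when an event changes severity: "Multiple AE records with differing attributes can comprise a single linked AE occurrence". For tables, the rule is "Linked AEs will be selected for analysis in tables based on their worst case scenario attribute", and the attributes named are "maximum CTC grade, causal relationship, seriousness, and treatment emergence out of all records".

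The same section expects a linked AE to span the start of treatment. It says "AE records within a linked AE can be given different treatment-emergence status", and sets the test as follows: "Treatment emergence for linked AEs will be established as those records in the linked AE with a worsening of severity from the preceding pre-treatment record". It then adds: "Any AE subsequently linked to an on-treatment AE would be considered treatment-emergent".

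SAP 10.15.1 defines a TEAE as an event that began or got worse after treatment started, and gives improvement of an existing condition as an example of what does not qualify. Protocol 9.3.3.1 defines a TEAE in nearly the same way. Protocol 8.3.2 collects AEs from consent, so pre-treatment AE records do exist.

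**The concern.** Treatment emergence is decided record by record, but the tabulated grade, relationship and seriousness come from every record of the linked AE. One treatment-emergent record brings the whole linked AE into the TEAE tables, and the event then shows a severity that may have been reached only before the first dose.

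The outputs at stake are in SAP 12.8.1.1: the grade 3 or higher TEAE tables, their SOT101-related and combination-related versions, and the tables by maximum grade. Read naturally, the rule maximises each attribute separately. A pre-dose grade 3 record judged not suspected and an on-treatment grade 2 record judged suspected would then combine into a grade 3 drug-related TEAE that no single record shows. Seriousness works the other way in one table: a serious flag on a pre-dose record would take an event out of the non-serious TEAE summary.

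**Working it through.** There is no stated figure to reproduce. The check applies the SAP's rules to short grade sequences.

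**Inputs**
- Attribute rule: maximum over all records (SAP 12.8.1).
- Emergence test: an on-treatment record is treatment-emergent if its grade exceeds that of the last pre-treatment record (SAP 12.8.1).
- Carry-forward: the last sentence of SAP 12.8.1 makes later linked records treatment-emergent and states no worsening condition. Two readings are possible: (a) it applies only after a treatment-emergent record; (b) it applies after any on-treatment record.

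**Sequences.** Each starts with a pre-dose grade 3, has one or two pre-dose and one or two on-treatment records, changes grade at every record, and stays below grade 3 on treatment. There are eight. The bar marks the first dose.

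| Sequence | Tabulated under (a) | Tabulated under (b) | Worst treatment-emergent record |
|---|---|---|---|
| 3 \| 1 | not a TEAE | not a TEAE | none |
| 3 \| 2 | not a TEAE | not a TEAE | none |
| 3 \| 2, 1 | not a TEAE | grade 3 TEAE | none (a); 1 (b) |
| 3 \| 1, 2 | not a TEAE | grade 3 TEAE | none (a); 2 (b) |
| 3, 1 \| 2 | grade 3 TEAE | grade 3 TEAE | 2 |
| 3, 1 \| 2, 1 | grade 3 TEAE | grade 3 TEAE | 2 |
| 3, 2 \| 1 | not a TEAE | not a TEAE | none |
| 3, 2 \| 1, 2 | not a TEAE | grade 3 TEAE | none (a); 2 (b) |

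**Result.** Under (a), 2 of 8 sequences are tabulated as grade 3 TEAEs with no on-treatment grade 3. Under (b), it is 5 of 8. Four sequences only ever improve (3 | 1; 3 | 2; 3 | 2, 1; 3, 2 | 1). Of these, none is misreported under (a) and one, 3 | 2, 1, under (b). These are counts of possible patterns, not expected frequencies.

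**Worked case.** For 3, 1 | 2, the last pre-dose grade is 1 and the on-treatment grade is 2. Since 2 > 1, the record is treatment-emergent under either reading. The tabulated grade is max(3, 1, 2) = 3; over treatment-emergent records alone it is 2.

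**After restricting attributes to treatment-emergent records.** None of the 8 is tabulated as grade 3. Under (b), however, 3 | 2, 1 would still appear, as a grade 1 TEAE, although it only improved. That conflicts with SAP 10.15.1, so the carry-forward sentence needs its own correction.

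**Size of one case.** In a cohort of 50 (planned for NSCLC and for ovarian cancer), 1/50 = 2.0 percentage points. SAP 6.1 says recruitment stopped after the August 2023 futility analysis, so cohorts may be smaller. If a cohort ended at its futility sample size (an assumption), one case is 1/21 = 4.8 points or 1/12 = 8.3 points.

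**The case against.** The strongest reply is that the pattern is rare and the harm limited. It needs a grade 3 record made after consent, within a screening period of at most 28 days (Protocol 4.1.1); a fall in grade without resolution; a patient who is still eligible and dosed; and a later worsening that stays below the screening grade. An event that resolves and recurs is documented separately (Protocol 8.3.8.2), so it would not be one linked AE. All of this stands, and it limits the frequency.

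A reader might infer several stronger things that the documents do not support:

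- *Any screening grade 3 that improved becomes a grade 3 TEAE.* It does not. A single lower on-treatment grade fails the worsening test in SAP 12.8.1 and is excluded by SAP 10.15.1.
- *Eligibility makes the pattern common.* Inclusion criterion 8 says "Must have recovered from all AEs (except alopecia) due to previous therapies to grade" 1 or lower, with an exception for stable grade 2 neuropathy. But it concerns toxicity of earlier therapy, much of which predates consent and so leaves no pre-treatment AE record to link.
- *Serious TEAE rates are inflated.* The SAE tables in SAP 12.8.1.2 that count patients with at least one SAE are not limited to treatment-emergent events, so a serious screening event counts there in any case. Treatment-emergent SAEs appear in the SAP as a listing, while the worst-case rule governs tables.
- *Every case adds a false count.* Patients count once per SOC or PT, so a patient with a genuine grade 3 or higher TEAE in that row adds nothing to it.

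It can also be said that the rule errs towards overstating toxicity, that the analyses are descriptive, and that all AEs are listed, so affected cases can be traced. This lowers the stakes but does not make the tabulated grade right. Nor does the rule always overstate: the non-serious TEAE table loses events.

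**Conclusion.** The point holds in a narrow form and is minor. It follows from a stated rule, not from missing detail. A linked AE that reached grade 3 after consent, improved before dosing and then worsened on treatment to a lower grade is tabulated as a grade 3 TEAE under either reading of the carry-forward sentence. The drug-related version follows if the on-treatment record is suspected and each attribute is maximised separately. Whether an event that improves continuously over two on-treatment records is also counted depends on how the carry-forward sentence is read, so two programmers could produce different tables.

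The number of cases cannot be computed, because the documents do not say how many linked AEs have pre-treatment records; it is probably small. The per-case figures assume a patient with no other grade 3 or higher TEAE in the same row.

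**What to change.** Make two changes in SAP 12.8.1:

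1. In TEAE tables, take maximum grade, relationship and seriousness only over the treatment-emergent records of the linked AE.
2. State that a later linked record becomes treatment-emergent by carry-forward only if it follows a treatment-emergent record, so that 3 | 2, 1 is not counted, in line with SAP 10.15.1.

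The cost is one phrase, one clarified sentence and a filter in the AE table programs. No new data are needed, because treatment emergence is already assigned record by record. If the tables have already been run, search the AE data for linked AEs with a treatment-emergent record and either a pre-dose grade above every treatment-emergent grade or a serious flag only before dosing. Also check linked AEs whose treatment emergence rests on the carry-forward sentence alone. Together these searches show whether any count changes.
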